## **Interventions and Materials**

**Caregiver Workbook.** The Caregiver Workbook will be sent to each participant after randomization. The Workbook will structure materials used by participants in the active intervention and additional material for the webinars, serve as a “central location” to place all materials, and provide a resource after study end. Modeled after those used in the REACH VA programs, the Workbook has patient disease and behavioral management topics, caregiver stress and coping topics, and additional resource material that expands on each topic. The Workbook has activities throughout, including worksheets related to each topic and questions to deepen participants’ interactions with the material and personalize issues. The Workbook also addresses red flag issues. During the individual and webinar sessions, the Interventionist will make participants aware of relevant red flags – areas that may exacerbate problems, add a level of difficulty or distress, and/or indicate a need for referrals – and highlight referral information and additional commercial or public resources (in the Workbook) that will expand on the particular didactic topic. Examples of Red Flags include Guide and Safety Plan for unsafe or dangerous behaviors; Abuse and Addictions – Finding help and assistance.

Supplemental materials we currently include in our spouse telephone groups Participant Workbooks include: Worksheets for activities, Relaxation Techniques, Signal Breath, Rate your tension level, Change Worksheet, Active Listening, and Crisis Hotline Numbers. Additional commercially available materials include: Suicide Prevention materials (Suicide Prevention Men and Women Veterans – Knowing the Warning Signs of Suicide – Brochure, magnet and warning signs card), Poison Help

stickers, Stress and PTSD materials (Stress, Job Stress, Let's Talk About Post Traumatic Stress Disorder, TBI and PTSD).

**Individual Sessions Arm.** The individual sessions intervention focuses on education, skills building, and support. It will be delivered in six sessions by telephone over three months. We will use the format that is used nationally in the VA in the REACH VA intervention for dementia and SCI/D caregivers.

The strength of the individual sessions intervention is that it is structured, standardized and targeted to help caregiver focus on what needs to be done in the short and long term, without being overwhelmed by the many challenges of care. The sessions are structured through a protocol that specifies activities to occur at each session. There are materials for staff in an Interventionist Manual including protocols, and scripts and talking points for each topic. The intervention is standardized to ensure that the five caregiving risk areas of safety, social support, problem behaviors, caregiver emotional well-being, and caregiver health are covered and core skills are taught.

Most importantly, however, the intervention is targeted and individualized to the concerns of the specific caregiver and care recipient through a risk assessment. The Risk Priority Inventory (RPI) assesses the main caregiving risk areas for the specific caregiving dyad. The RPI is used to tailor the intervention for care recipient behaviors or safety issues and/or caregiver centered issues/concerns related to health, physical and emotional well being, and/or social support.

The individual sessions incorporate evidence-based components that are crucial to successful caregiving interventions (36,21,37) including problem solving, cognitive restructuring/mood management, and stress reduction. The Interventionist and caregiver negotiate the concerns to be addressed using those identified by the risk assessment. Using problem solving techniques, Interventionist and caregiver attempt to find effective and workable solutions to a specific target behavior/issue that is causing stress and burden for the caregiver. The target behavior/issue could be something related to the caregiver, such as asking family members for help, or to the care recipient, such as bathing or driving. In this way the intervention accommodates whatever concern the caregiver is experiencing – from ADL challenges for seriously compromised service members to risky behaviors of service members with mild TBI or PTSD, or to caregiver stress, guilt or grief.

The Interventionist teaches the ABC (Antecedent, Behavior, Consequences) method of problem solving and the caregiver and Interventionist identify action-oriented behavioral strategies to address caregiving problems or patient behaviors using topics from the Caregiver Workbook in a targeted behavior/issue plan. Problem solving steps include:

1. Determine problem
  - Patient behavior
  - Caregiver reaction or concern
2. Define/operationalize the problem
  - Frequency
  - Duration
  - Intensity
  - Characteristics
  - Antecedents and consequences of behavior (ABC Process)
3. Assess previous attempts to address
4. Set goals and realistic outcome
5. Treat or eliminate antecedents and triggers
  - Unmet physical needs (e.g., pain)
  - Unmet psychological needs (e.g., loneliness)
  - Environmental causes (e.g., stimulation, noise)

- Psychiatric causes (e.g., depression)

6. Develop plan
  - Brainstorm best practice and evidence-based strategies, using the Caregiver Notebook
  - Help caregiver select strategies based on problem type and dyad's needs, abilities, and resources
  - Write strategies down
  - Teach caregiver to use strategies, practice and role model
7. Review and troubleshoot plan

The plan is implemented by the caregiver and revisited at the next session to discuss success, failure, barriers, and/or need for modification. At each session following the introduction of the target behavior/issue plan the Interventionist reviews the suggestion and strategy implementation by the caregiver (i.e., what have you tried) and the status of the behavior/issue (i.e., goal attainment, better, worse, the same).

The Interventionist also provides training on cognitive restructuring using caregiver identified concerns and stress management techniques such as signal breath, stretching, guided imagery, and pleasant events. Training in skills for managing caregiver mood and behavior focuses on two overarching approaches: reducing negative affect/mood and increasing positive affect/mood. The Interventionist helps the caregiver reduce negative affect/mood (frustration/anger and sadness/depression) by learning to appraise the situation more realistically and learning to identify and challenge negative thinking. The Interventionist also works with the caregiver to increase positive mood through an awareness of the connection between mood and activities, learning to relax in the stressful situation and manage stress, along with strategies for increasing simple everyday pleasant activities.

Each session is structured to build on the previous session using a protocol. Although tasks are structured and pre-determined (e.g., problem solving), the focus of the task is a risk area (e.g., safety), concern (e.g., lack of support), or patient problem (e.g., angry outbursts) that the caregiver has identified as troubling.

### **Session 1**

- Review caregiver Risk Priority
- Ask caregiver to tell story
- Introduce intervention
- Review Caregiver Notebook
- Discuss effects of stress
- Introduce stress management technique, Signal Breath
- Obtain closure to session

### **Session 2**

- Introduce session
- Review/modify Signal Breath stress management technique
- Provide general education about patient's condition, as needed
- Present safety material (including alerts if appropriate)
- Introduce health care issues (including alert if appropriate)
- Introduce Health Guide designed to help manage health care and develop healthy habits
- Introduce target behavior/issue plan #1
- Obtain closure to session

### **Session 3**

- Introduce session
- Review/modify target behavior/issue plan #1

- Introduce cognitive restructuring/mood management
- Obtain closure to session

#### **Session 4 and Session 5**

- Introduce session
- Review/modify mood management or stress management technique
- Determine caregiver goal attainment for target behavior/issue #1 (better, the same, worse, and barriers)
- If needed, review/modify target behavior plan #1
- If appropriate, problem solve - identify target behavior/issue #2
- Introduce target behavior/issue plan #2
- If needed, modify target behavior/issue plan #2 (Session 5)
- Offer stress management technique, Power of Music, Stretching or Pleasant Events
- Obtain closure to session

#### **Closure Session**

- Introduce session
- Review use of Health Guide and safety recommendations
- Review target behavior/issue plans covered and strategies that worked
- Review cognitive restructuring/mood management techniques
- Review stress management techniques and strategies that worked
- Validate caregiver use of strategies
- Encourage use of available formal and informal support services
- Obtain closure

**Education Webinar Sessions Arm.** One common type of control condition involves equal attention without the therapeutic components being tested in the intervention condition. Attention control tests the hypothesis that improvements in the outcome occur because of participant expectancies and the attention received during the course of the treatment, rather than from the treatment itself (65,66). For the education webinar sessions, topics addressing each of the caregiving risk factors topics but without the skills building or cognitive restructuring components present in the individual intervention sessions will be available online in webinars. The education webinar sessions will focus on general information safety, social support, problem behaviors, caregiver emotional well-being, and caregiver health. Education webinar session participants will also receive the Workbook.

Each individual assigned to the education webinar arm will be called and informed how to access the session through the VA Memphis website, using a participant code. This code will be specific to the individual participant, but will not contain any identifiable information. Once a participant logs in to view the session an email will be sent back to the Interventionist to let her/him know who did, or did not, view each topic. The Interventionist will send a reminder email every two weeks to notify education webinar participants that a new session is ready to be viewed. In our current study of OEF/OIF/OND spouses, all spouses have had internet access and have expressed a preference to be contacted through the internet. Paper copies of slides can be sent to individuals who request them.

Each session will last approximately thirty minutes through PowerPoint slide presentation format. The education webinar sessions are pre-recorded by an Interventionist to reduce information variability to improve consistency. For maximum flexibility for participants, once the session has been uploaded to the Spouse/Family Support website the session can be viewed at any time during the two weeks the webinar is available. We will examine number of sessions viewed by each participant as dosage in analysis.

**Interventionists Training and Certification.** The Interventionists will be masters level healthcare or mental health experienced clinician/educators. As we currently do in the REACH VA national clinical program, each will be trained with didactic and hands on content, knowledge assessment, skills practice, and role playing for certification. The Interventionist will use a mock caregiver to complete a role play of two key areas of the intervention: identify and introduce target behavior/issue plan, and mood management/cognitive restructuring. Based on observation of the role play at least two senior investigators will complete the Certification Role Play Observation Checklist for Individual Sessions. The checklist includes behaviorally anchored ratings of specific procedural techniques (e.g., correct use of forms) and clinical skills (e.g., active listening). Performances are observed for content and process until two investigators give marks of 90 to 100% on the treatment fidelity form. Feedback is individually provided for each of the items listed on the Checklist. Structure of the feedback includes: statement(s) about any positive behavior demonstrated; statement(s) about what behaviors should have occurred or occurred and were not in keeping with the protocol; then rationale for the behavior that was expected. Feedback will also include “Required Activities” that must be completed before certification can be granted. Any item scored as a zero on the checklist will automatically result in a required activity.

[figure not shown]
Training for Interventionists will include strategies for overcoming problems associated with telephone interactions such as decreased cues and technological difficulties. These strategies include behaviors such as use of prompts/open ended questions to solicit information; use of rephrasing, reflection, summarization; use of participant’s own language/descriptors; active listening (e.g., summarize comments correctly); assessment of participant’s understanding of the intervention by “checking in” and by asking questions; appropriate level of assertiveness (e.g., guides the intervention according to protocol, redirects participant appropriately as needed); and use of empathetic responses while remaining on protocol.

**Treatment Fidelity Assessment.** To assess intervention benefit accurately, it is necessary to determine whether the intervention is being delivered as intended, whether participants are hearing and understanding, and whether participants are acting on the intervention. This has been lacking in previous trauma research (67). For the active intervention arm we will assess delivery, receipt, and enactment using direct and indirect measures and a quantitative assessment (68) as we have in our past and current research (69). The investigators will listen to the sessions, all of which are taped. We will score all sessions in the early stages until satisfactory performance standards (90% range consistent scores) are met, and continue to check sessions throughout the study to assess maintenance or drift in integrity. Reliability checks will be conducted on 25% of the scored tapes by an independent second rater.

For Delivery Assessment, for each session, there are components that are intended (positive) and plausible confounding parts that should not occur (negative). Positive score minus negative score yields the overall session evaluation score. Receipt Assessment is accomplished by determining whether the participant understands the materials. For delivery and receipt, raters listen for specified cues. Enactment is assessed at the following session, using the same scoring procedure. Enactment allows a determination of which suggestions were tried, which were most helpful for specific problems, and which do not work for certain problems and certain participants. Follow-through on target behavior/issue plans will determine enactment.

## Participant Identification and Recruitment

Study Flow Chart

There will be multiple avenues of recruitment, as we have utilized in our previous DoD and VA studies for deployed and post deployment spouses and dementia and spinal cord injury/disorders caregivers, all of which have exceeded recruitment goals. Several military and military family websites routinely post our information so that potential participants can contact us directly. As we routinely do, we will contact VHA staff who work with post 9/11 veterans and caregivers, including Caregiver Support Coordinators and OEF/OIF/OND Program Managers. Each VA facility has these positions and we have access to national mail groups and national education sessions that target each group. The VA's Polytrauma System of Care will be a major source of referrals; this system of care includes Polytrauma/TBI care and staff at each facility, including transitional residential inpatient care and local clinics (see <http://www.polytrauma.va.gov/index.asp>).

We will also have a website hosted on the VAMC Memphis internet site similar to our current study information (<http://www.memphis.va.gov/spousesupport/>), a blurb on the VAMC Memphis Facebook page (<https://www.facebook.com/MemphisVAMC>), and a Twitter page (<https://twitter.com/MemphisVAMC>).

**Telephone Screening and Participant Consent.** As shown in the flow chart, within one week of receiving an inquiry from a potential participant or a referral, a Research Associate will telephone to screen the participant. This is the process we currently use successfully.

- Participants must give permission to be screened after hearing a study description that includes the components of informed consent, including information about the research study and the screening process itself. Research study components include a statement of the research (purpose, procedures), reasonably expected benefits to subjects or others, and costs. Screening process components include duration of screening, alternatives, extent of confidentiality, and authorization for release of protected health information for research purposes.
- After screening, consent forms, signed by the person who will be obtaining consent, are mailed to the participant with a post-paid return envelope. Written informed consent from the participant is an integral part of the study. Informed consent will follow the procedures of the IRB and Research and Development (R&D) Committee of the VAMC Memphis. All participants **must** give written informed consent before becoming study participants and assent must be obtained from the service member and reported by the participant.
- During the informed consent call the potential participant will be asked to read the informed consent and be given the opportunity to ask questions. A Research Associate will review all key aspects of the study with the potential participant. Staff will question to ascertain whether the potential participant has understood the information. Potential participants who are illiterate or have impaired vision will have the consent read to them and will be given an opportunity for questions and discussion. A signed informed consent is required prior to data collection. Participants will be encouraged to ask for clarification about the forms and discuss concerns about the study at this time.
- The consent form is carbon color coded. After the participant initials and signs the form, one copy of each page is kept by the participant, and one is filed in the study office. To protect participant confidentiality and per IRB waiver, no witness is required.
- After consent is obtained and baseline data collection, the Data Analyst (DA) will randomly assign each participant to one of the study arms. Participants are independently assigned to study arms and there will be no stratification based on covariates at the time of assignment to study arm. The DA will maintain a confidential, locked register of names, study identification numbers, and treatment arm assignments.

- As soon as baseline data collection and randomization are completed for a participant, a staff member will call and provide information on assignment and the intervention.

**Retention.** Because all interaction is by telephone, travel will not affect retention. We offer \$25 for each completed data collection call to offset time required (baseline, three and six months, project evaluation) for a total of \$100. In our work with spouses of post 9/11 service members, lost to follow-up rates are 17 to 20%. For our caregiver intervention studies, lost to follow-up rates are lower, around 10% (70).

**Alerts/Adverse Event Protocols.** Alerts may be recognized during data collection, outside scheduled contacts, and during intervention sessions. Alerts/adverse event standardized procedures will be those we currently use for post deployment spouses and caregivers. Alerts include suicidal ideation, increased alcohol/drug use, and clinical depression levels plus dangerous patient behaviors. Our current procedure ensures that any alert be discussed immediately with [name] and appropriate action taken, based on standardized procedures. For example, in our current study, for clinical depression levels, we follow up with the participant who is also advised to contact her physician or other resource. All alert events are recorded on the Project Alert Form that includes event date, whether event is treatment related, and date event was addressed. The form is given to [name] within 24 hours of learning of the event and the event documented by the appropriate staff member in progress notes, and reported to IRB, if appropriate. Alerts, adverse events, and referrals will not cause a participant to be dropped from the study, but will be considered in analysis. Any contact outside group or data collection will be documented (time, reason, actions taken, initiator) on the Delivery Assessment tracking form.

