## **Data Collection and Variables**

**Research Associates Training and Certification.** Training for Research Associates (RA), who will be masters prepared, will include interviewing over the telephone, asking sensitive questions, use of study instruments, five practice interviews, and a final certifying audiotaped interview with a volunteer participant. The investigators and each RA rate responses on three mock interviews to determine inter-rater reliability. RAs will be evaluated on their conduct during data collection interviews. The Researcher Evaluation Form is scored by the investigators using recorded calls. Scores are determined by 1) those things executed (e.g., asks questions as written, probes consistently and only when necessary) and 2) negative items (e.g., volunteers personal information that may bias answers, uses directional probes), with 100 being a perfect score and 90 being acceptable. After training, periodic checks of RA performance are conducted.

**Data Collection.** Data collection will occur at baseline, 3, and 6 months post randomization by telephone. All calls are recorded. Data collection takes approximately 45 minutes, based on our current telephone data collection with caregivers and OEF/OIF/OND spouses, using the same and similar instruments. We send response cards to the participant to make answering more efficient. The same masked RA performs all data collection for a participant.

Measures (shown below) were specifically chosen 1) to capture the mechanisms of action related to the theoretical model for individual stress process, and 2) to map onto measures being used by DoD and VHA clinicians and researchers to provide maximum utility and generalizability for the study results. Independent measures have been selected to characterize the study sample and to assess factors that have potential to impact the outcome measures. Many of the instruments and concepts are used in the Rand study of military caregivers (23), or were developed for use in research with OIF/OEF/OND family members, using expert panel input and focus group interviews (71). We are using several of these outcomes and instruments in our two current military spouse studies and our REACH VA clinical program.

Category	Name of Measure/Form	Battery (B) Screening (S)
----------	----------------------	------------------------------

		Risk Priority Inventory (RPI)
Depression	Patient Health Questionnaire (PHQ-9)	B
Anxiety	Generalized Anxiety Disorder (GAD-7)	B

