We build the mixed-effects models by a forward selection procedure for the covariates of particular interest to us. Because over-parameterization is a concern in this analysis, we will give priority to covariates that are individually contributing to the model fit (evaluated by significance of parameters in the model as well as AIC and SC) and are (if possible) independent of each other. To improve model fitting we will center or standardize some or all covariates. Interaction terms will be included as needed.

We investigate intervention effectiveness by comparing the slope of the linear fits for individuals that were assigned to individual sessions with the slope of individuals that were assigned to the webinars. A mixed-effects model contains *fixed effects* and *random effects*. The mixed-effects model allows us to study whether other variables are an important factor for the development of the primary outcomes. Besides the indicator of individual  $i$  intervention assignment and demographic information such as race, age, or rural/urban location, covariates of interest to us are the participant's family composition, participant gender, and the general social support the caregiver receives. We also collect the participant's perception of the patient's disability at baseline (WHODAS 2.0 level of disability from 0 to 100) and will investigate the role that covariate might play in each model. These questions will be addressed by investigating the statistical significance of the corresponding parameters in the fitted mixed-effects model. SPSS will be used for analysis.

In addition, we will investigate possible drop out patterns in the data. This is, however, an exploratory part of our analysis and we will assume that measurements are *missing at random* in the primary analysis.

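### Nobody who analyses the data is masked to arm, and the mixed models that judge effectiveness are chosen from the data; fix the models in advance or choose them with the arm variable withheld

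*Combined protocol and SAP*

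**What the plan says.** **Assignment and custody.** Under Participant Identification and Recruitment (Telephone Screening and Participant Consent), after consent and baseline data collection "the Data Analyst (DA) will randomly assign each participant to one of the study arms". The next duty falls to the same role: "The DA will maintain a confidential, locked register of names, study identification numbers, and treatment arm assignments". Assignment is independent for each participant, and "there will be no stratification based on covariates at the time of assignment to study arm".

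**Masking.** Data Collection and Variables states: "The same masked RA performs all data collection for a participant". No section describes a masked analyst, coded arm labels, an independent statistician or a model lock.

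**Model building.** Under Mixed-Effects Modeling Approach, effectiveness is investigated by comparing fitted slopes between arms, with a separate model for each primary outcome. On the choice of terms: "We build the mixed-effects models by a forward selection procedure for the covariates of particular interest to us". The criteria are given as "evaluated by significance of parameters in the model as well as AIC and SC", without a threshold, an order of entry or a rule for when they disagree. Centring or standardizing may be applied to some or all covariates, and "Interaction terms will be included as needed". The covariate list is illustrative, not closed. The Hypotheses section adds sessions completed, amount and type of care, and type of injury.

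**The other analysis.** Data Analysis and Sample Size and Statistical Power also plan a repeated-measures ANOVA testing group by time. No covariates are specified for it. The plan does not say whether the ANOVA or the mixed model decides.

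**The concern.** Participants know which programme they receive, and they report all three primary outcomes themselves. Masking at the analysis stage is therefore one of the few protections against bias still available, and the plan does not claim it.

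Two conditions together create the risk: access to arm, and freedom over which terms enter the model. The plan allows both. With unstratified assignment, chance covariate imbalance is to be expected, so different sets of terms will move the between-arm slope by different amounts. Someone who sees arm while choosing terms can, deliberately or not, settle on the set that gives the more favourable result.

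The timetable adds to this. In the Statement of Work, data collection and cleaning run to month 35 while analysis starts in month 28, an overlap of eight months (28 to 35), with no stated point at which data and model are frozen.

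**Working it through.** The plan gives no figure to reproduce here. The check sets the text side by side and then asks how large the effect could be.

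**1. Who could know arm while choosing the model?** The role titled Data Analyst makes the assignments and holds the register. The analysis sections say only 'we'. Data entry and cleaning (Statement of Work, Task 7) are assigned to no role. So the text establishes that no analyst is masked; it does not establish who the analyst is.

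**2. Which choices can move the slope comparison?**
- With measurements at 0, 3 and 6 months, a participant's least-squares slope is (−3·Y0 + 0·Y3 + 3·Y6)/18 = (Y6 − Y0)/6. With complete data the slope comparison is therefore a comparison of gain scores.
- A covariate entered only as a main effect leaves that contrast unchanged when all three measurements are present. It moves the contrast when it enters with a time interaction, which the open interaction clause permits.
- Centring alone does not change the slope test. It matters only once an interaction lets the arm effect on slope vary with the covariate, because the arm-by-time coefficient is then read at the centring point.

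**3. Size under the null.** From the plan: 80 per arm less 20% attrition, 80 × 0.80 = 64 per arm; two-sided 0.05. Assumed, because the plan does not give them: 5 or 8 candidate covariates, jointly explaining 10% or 30% of gain-score variance. The model is linear on the gain score, with 1,500 simulated trials per setting. Entries are type I error for one outcome.

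| Candidates, variance explained | Covariates fixed in advance | Forward selection, arm left out | Covariates picked to favour an arm difference | Same, plus one interaction and a free centring point |
|---|---|---|---|---|
| 5, 10% | 0.050 | 0.049 | 0.098 | 0.359 |
| 5, 30% | 0.047 | 0.043 | 0.149 | 0.463 |
| 8, 10% | 0.049 | 0.047 | 0.111 | 0.527 |
| 8, 30% | 0.049 | 0.053 | 0.187 | 0.638 |

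The simulation standard error is √(0.05 × 0.95/1500) = 0.0056 at 0.05 and √(0.187 × 0.813/1500) = 0.010 at the top of the covariate-only range. The second and third columns are therefore compatible with 0.05; the fourth is not. The last column is an extreme search and marks an outer limit only.

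**4. Would A/B coding cure it?** In a further null simulation (7 covariates, 64 per arm, search over all subsets), the chance of a false claim of benefit was 0.084 with arms known and 0.084 with A/B labels, against a nominal 0.05/2 = 0.025 in that direction. A two-sided p-value is unchanged when labels are swapped, so coding hides the direction but not the p-value. Forward selection with the arm variable left out held the two-sided error at 0.049.

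**The case against.** The strongest reply is that the plan is less open than it looks. Selection has stated criteria, so it is not a free search, and "Because over-parameterization is a concern in this analysis, we will give priority to covariates that are individually contributing to the model fit" shows an intention to keep the models small. Selection on those criteria without regard to arm did no harm in the simulation. The trial is sized on the ANOVA, which has no covariates to choose, and the intention-to-treat commitment limits later choice of population. All of this stands. It confines the problem to the mixed models. It does not remove it, because those models are also used to judge effectiveness, the criteria can disagree with no rule to settle it, and interactions are open.

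Three stronger readings are tempting, and the documents do not support them:
- **That the Data Analyst cleans the data and fits the models.** This is an inference from the job title and from no other analyst being named.
- **That the register is closed to everyone except the analyst.** The plan says only that it is confidential and locked. Another staff member calls each participant with the assignment, so others know arms too.
- **That the number of possible covariate subsets measures the bias.** The plan describes forward selection, not a search of all subsets, and a count of models is not an error rate.

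**Conclusion.** The point holds in limited form. The plan lets whoever builds the mixed models know arm, and leaves them enough discretion for that knowledge to affect the between-arm slope test. The ANOVA is unaffected.

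In the worst-case covariate search the type I error per outcome is about 0.10-0.19 instead of 0.05. That range rests on the assumed number and strength of covariates, on covariates entering in a way that affects the slope, and on choices made to favour an arm difference. It shows what the plan permits and does not predict what the analyst will do. Fixing the terms in advance, or selecting them without the arm variable, keeps the error near 0.05. The weakness should be corrected before the data are analysed; it does not show that any result is biased.

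**What to change.** **1. Mixed-Effects Modeling Approach.** For each primary-outcome model, fix the covariates, interactions and centring in advance. If selection from the data is kept, carry it out on a data set from which the arm variable and fields that reveal arm are withheld. These include session counts and the fidelity scores, which are planned for the active arm only. Lock the data and the model, and only then add arm and arm-by-time. State the entry threshold and which criterion prevails. Do not rely on A/B labels alone.

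**2. Participant Identification and Recruitment.** Have an existing staff member who neither analyses data, collects outcomes nor enrols participants hold the register until that lock. State who fits the models and that this person is masked until then.

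**Cost.** Sample size, visits and interventions do not change. The plan gains a short lock procedure and one task moves between staff; the documents do not show who is free to take it. Session-count checks before lock must be done by someone other than the analyst. Under the selection route, sessions completed, which the Hypotheses section lists for adjustment, cannot be examined until after lock; the exploratory compliance analysis can wait until then.
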